11.3.2 Diarrhea

Episodes of diarrhea have occurred in patients receiving trametinib and erlotinib (package insert). Other frequent causes of diarrhea may include concomitant medications (e.g., stool softeners, laxatives, antacids, etc.), infections by *C. difficile* or other pathogens, or partial bowel obstruction. Those conditions should be excluded.

Guidelines regarding management and dose modification for diarrhea considered related to trametinib and/or erlotinib are provided in the table below.

Management and Trametinib /Erlotinib Dose Modification Guidelines for Diarrhea		
CTCAE Grade	Adverse Event Management	Action and Dose Modification
Grade 1 or 2	
 • Diet: Stop all lactose containing products; eat small meals, BRAT-diet (banana, rice, apples, toast) recommended. • Hydration: 8-10 large glasses of clear liquids per day (e.g., Gatorade or broth). • Loperamide¹: Initially 4 mg, followed by 2 mg every 4 hours or after every unformed stool; maximum 16 mg/day. Continue until diarrhea-free for 12 hours. • Lomotil¹: 2.5-5mg of diphenoxylate up to 4x a day; maximum 20mg/daily. Continue until diarrhea-free for 12 hours. • Diarrhea >24 hours: Loperamide 2 mg every 2 hours; maximum 16 mg/day. Consider adding oral antibiotics. 	
 • Continue trametinib and erlotinib at same dose. Initiate adverse event management
Grade 3 diarrhea	
 • Clinical evaluation mandatory. • Loperamide¹: Initially 4 mg, followed by 2 mg every 4 hours or after every unformed stool; maximum 16 mg/day. Continue until diarrhea-free for 12 hours. • Lomotil¹: 2.5-5mg of diphenoxylate up to 4x a day; maximum 20mg/daily. Continue until diarrhea-free for 12 hours. 	
 • Interrupt trametinib and or erlotinib until diarrhea resolves to ≤ grade 2. • Restart treatment at same dose or with a dose reduction at discretion of investigator.²
Grade 4	
 • Oral antibiotics and second-line therapies if clinically indicated • Hydration: Intravenous fluids if clinically indicated. • Antibiotics (oral or intravenous) if clinically indicated. • Intervention should be continued until the subject is diarrhea-free for ≥24 hours. • Intervention may require hospitalization for subjects at risk of life-threatening complications. 	
 • Withhold trametinib and erlotinib until toxicity is grade ≤=2. Initiate adverse event management. Discontinue permanently or restart with a dose reduction at the discretion of the investigator.²

1. Loperamide and Lomotil should be made available prior to start of study treatment so loperamide administration can begin at the first signs of diarrhea.
 
2. Escalation of trametinib to previous dose level is allowed after consultation with the medical monitor and in the absence of another episode of complicated or severe diarrhea in the 4 weeks subsequent to dose reduction.
		

11.3.3 Pneumonitis

Pneumonitis has been observed in patients receiving trametinib and erlotinib. To reduce the risk of pneumonitis, patients will be monitored closely for symptoms and evaluated with imaging and functional tests. Dose modification and supportive care guidelines for pneumonitis are described in the tables below.

CTCAE Grade	Adverse Event Management	Action and Dose Modification
Grade 1	
 • CT scan (high-resolution with lung windows) recommended • Clinical evaluation and laboratory work-up for infection • Monitoring of oxygenation via pulse-oximetry recommended • Consultation of pulmonologist recommended 	
 • Continue trametinib/erlotinib at current dose if clinically indicated.
Grade 2	
 • CT scan (high-resolution with lung windows) • Clinical evaluation and laboratory work-up for infection • Consult pulmonologist • Pulmonary function tests –if < normal, repeat every 8 weeks until ≥ normal • Bronchoscopy with biopsy and/or BAL recommended • Symptomatic therapy including corticosteroids if clinically indicated 	
 • Interrupt trametinib/erlotinib until recovery to grade ≤1 • Consider restarting with trametinib/erlotinib reduced by one dose level • Escalation to previous dose level after 4 weeks and consultation with medical monitor possible • If no recovery to grade ≤1 within 4 weeks, permanently discontinue study treatment
Grade 3	
 • CT scan (high-resolution with lung windows) • Clinical evaluation and laboratory work-up for infection • Consult pulmonologist • Pulmonary function tests- if < normal, repeat every 8 weeks until ≥ normal • Bronchoscopy with biopsy and/or BAL if possible • Symptomatic therapy including corticosteroids as clinically indicated 	
 • Interrupt trametinib/erlotinib until recovery to grade ≤1 • After consultation with medical monitor, study treatment may be restarted reduced by one dose level • If no recovery to grade ≤1 within 4 weeks, permanently discontinue study treatment
Grade 4	
 • Same as grade 3 	
 • Permanently discontinue trametinib/erlotinib

11.3.4 Reduced Left Ventricular Ejection Fraction

Decreases of the left ventricular ejection fraction (LVEF) have been observed in patients receiving trametinib. Therefore, ECHOs must be performed in regular intervals outlined in the Study

Calendar. The same procedure (either ECHO or MUGA, although ECHO is preferred) should be performed at baseline and at follow-up visits

Trametinib Dose Modification Guidelines and Stopping Criteria for LVEF Decrease		
Clinic	LVEF-drop (%) or CTCAE grade	Action and Dose Modification
Asymptomatic	Absolute decrease of >10% in LVEF compared to baseline and ejection fraction below the institution's LLN.	
 • Interrupt trametinib and repeat ECHO within 2 weeks.^a • If the LVEF recovers within 4 weeks (defined as LVEF \geqLLN and absolute decrease \leq10% compared to baseline): 
 – Consult with the trametinib medical monitor and PI and request approval for restart. – Restart treatment with trametinib at reduced dose by one dose level^b – Repeat ECHO 2, 4, and 12 weeks after re-start; continue in intervals of 12 weeks thereafter. • If LVEF does not recover within 4 weeks: 
 – Consult with cardiologist. – Permanently discontinue trametinib. – Report as SAE – Repeat ECHO after 2, 4, 8, 12, and 16 weeks or until resolution.

Trametinib Dose Modification Guidelines and Stopping Criteria for LVEF Decrease		
Clinic	LVEF-drop (%) or CTCAE grade	Action and Dose Modification
Symptomatic^b	
 • Grade 3: resting LVEF 39-20% or >20% absolute reduction from baseline • Grade 4: Resting LVEF ≤20%. 	
 • Permanently discontinue trametinib. • Report as SAE. • Consult with cardiologist. • Repeat ECHO after 2, 4, 8, 12, and 16 weeks or until resolution.

^a If ECHO does not show LVEF recovery after 2 weeks, repeat ECHO 2 weeks later.
 
^b Escalation of trametinib to previous dose level can be considered if LVEF remains stable for 4 weeks after restarting of trametinib. Approval from GSK Medical Monitor is required.
 
^c Symptoms may include: dyspnea, orthopnea, and other signs and symptoms of pulmonary congestion and edema.
		

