6.1 CRITERIA FOR SUBJECT ELIGIBILITY

6.2 Subject Inclusion Criteria

All patients must have:

- Pathologic evidence of advanced stage IV or recurrent lung adenocarcinoma reviewed at MSKCC
- Somatic activating mutation in EGFR Radiographic progression during treatment with erlotinib or any other EGFR TKI therapies.
- Any number of prior chemotherapy regimens is permitted.
- Measurable (RECIST 1.1) indicator lesion not previously irradiated
- KPS \geq 70%
- Age $>$ 18 years old
- Must have undergone biopsy after development of acquired resistance to erlotinib with available archived tissue (equivalent of \geq 10 unstained slides)
- Left ventricular Ejection Fraction \geq the lower limit of normal by ECHO or MUGA
- Adequate organ function:
 - - AST, ALT \leq 2.5 x ULN

- - Total bilirubin $\leq 1.5 \times \text{ULN}$
- - Albumin $\geq 2.6 \text{ g/dL}$ - Creatinine $< 1.5 \times \text{ULN}$ OR calculated creatinine clearance $\geq 50 \text{ mL/min}$
- - Absolute neutrophil count (ANC) $\geq 1,200 \text{ cells/mm}^3$
- - Hemoglobin $\geq 9.0 \text{ g/dL}$
- - Platelets $\geq 100,000/\text{mm}^3$

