A maximum of two trametinib dose level reductions are allowed. If a third dose level reduction is required, treatment will be permanently discontinued.

Trametinib Dose Modification for Toxicities Not Specified in Subsequent Sections

Trametinib Treatment Modification for Clinically Significant Toxicities Deemed Related to Trametinib (This section is not for specific AEs such as rash, pneumonitis, diarrhea, liver chemistry, QTc prolongation, or visual changes. Refer to other sections for these specific AEs).		
CTCAE v4 Grade	Dose Modification	Management Guideline
Grade 1	Continue trametinib at current dose level.	Monitor as clinically indicated. Provide supportive care according to institutional standards
Grade 2	
 Consider interrupting treatment until resolution to grade 1 or baseline. Upon resolution, restart treatment at current dose level. 	
Grade 3	
 Interrupt trametinib if clinically indicated When toxicity resolves to Grade 1 or baseline, restart trametinib reduced by one dose level. If the Grade 3 toxicity recurs, interrupt trametinib; When toxicity resolves to grade ≤1, restart trametinib reduced by another dose level 	
Grade 4	
 Interrupt treatment until resolution to grade ≤1 Upon resolution to grade ≤1, restart with one level of dose reduction. If toxicity does not resolve to ≤1 or baseline, permanently discontinue trametinib. 	
Trametinib should be discontinued if treatment delay is ≥21 days due to toxicities. If the investigator concludes that continued trametinib will benefit a patient, the study PI and GSK medical monitor may be consulted for the possibility of resuming trametinib, provided that toxicities have resolved to grade ≤1.		

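### The LVEF table gives no instruction for a symptomatic fall of more than 10 and up to 20 points to below LLN but above 39%, although the same fall without symptoms requires trametinib to be stopped

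*Combined protocol and SAP*

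**What the plan says.** The table in Section 11.3.4 (Reduced Left Ventricular Ejection Fraction) sorts patients first by symptoms and then by LVEF.

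- **Asymptomatic row.** The trigger is "Absolute decrease of >10% in LVEF compared to baseline and ejection fraction below the institution's LLN". The action begins "Interrupt trametinib and repeat ECHO within 2 weeks". If LVEF recovers within 4 weeks, trametinib may restart one dose level lower after approval from the medical monitor and the principal investigator. If it does not recover, trametinib stops for good, a cardiologist is consulted and the event is reported as an SAE.
- **Symptomatic row.** The triggers are "Grade 3: resting LVEF 39-20% or >20% absolute reduction from baseline" and "Grade 4: Resting LVEF ≤20"%. The action is permanent discontinuation, an SAE report, a cardiology consultation and serial echocardiograms.

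No other row or footnote deals with a symptomatic patient below Grade 3.

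Section 11.2 has a general trametinib table for toxicities that later sections do not cover. LVEF has its own later section, but it is missing from that table's list of named exceptions, so a site might turn to the table. Its Grade 2 row says "Consider interrupting treatment until resolution to grade 1 or baseline", with restart at the current dose. Its Grade 3 row says "Interrupt trametinib if clinically indicated", with restart one level lower after resolution to Grade 1 or baseline.

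Entry requires LVEF at or above "the lower limit of normal by ECHO or MUGA" (Section 6.2). Footnote 5 of Table 10.1 schedules echocardiograms at screening and every three cycles, with a window of 2 weeks either side.

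**The concern.** Symptoms should make the response to a falling LVEF stricter. Read literally, this table does the reverse over part of its range. Of two patients with identical baseline and current values, the one without symptoms must stop trametinib and be re-imaged within 2 weeks, while the one with dyspnea has no LVEF-specific instruction.

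This is out of step with the protocol's other tables. In the hypertension table (Section 11.3.7), interruption is left to clinical indication in asymptomatic Scenario B and becomes unconditional in symptomatic Scenario C. The pneumonitis and visual-change tables (Sections 11.3.3 and 11.3.6) run from Grade 1 to Grade 4 without a break. The LVEF gap therefore looks like a drafting oversight.

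The situation can plausibly arise. Section 11.3.4 acknowledges LVEF decreases on trametinib and counts dyspnea as a symptom, and Sections 11.1 and 11.2 list shortness of breath as a toxicity of both drugs. At stake is a minimum safety rule for patients, not the efficacy result.

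**Working it through.** The plan states no figure to reproduce. The check is whether the two rows leave any LVEF values uncovered, and how wide that band is.

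**Inputs.** Let B be baseline LVEF and x current LVEF, both in %.

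- Asymptomatic row, value trigger (Section 11.3.4): B − x > 10 and x < LLN.
- Symptomatic row (Section 11.3.4): x ≤ 39 or B − x > 20. Grade 4, at x ≤ 20, lies inside this.
- Entry (Section 6.2): B ≥ LLN.
- LLN: not given in the protocol. Assumed to be 50% or 55%, with 53% as an intermediate value.

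**Uncovered set.** A symptomatic patient meets the first row's values but neither symptomatic grade when 10 < B − x ≤ 20, x < LLN and x > 39. In whole numbers, x runs from max(B − 20, 40) to min(B − 11, LLN − 1).

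**Worked example.** B = 60, x = 45, with dyspnea.

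- Fall = 60 − 45 = 15, which is more than 10, and 45 is below an LLN of 50 or 55. The first row's value trigger is met, but its label excludes the patient.
- 15 is not more than 20 and 45 is not 39 or lower. The second row is not met.

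**Width of the band.**

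| Baseline B | LLN 50%: uncovered x | LLN 55%: uncovered x |
|---|---|---|
| 50 | none (40 to 39) | not eligible |
| 55 | 40-44 (5 values) | 40-44 (5) |
| 60 | 40-49 (10) | 40-49 (10) |
| 65 | 45-49 (5) | 45-54 (10) |
| 70 | none (50 to 49) | 50-54 (5) |
| 75 | none | none (55 to 54) |

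Coding both rows as rules and running every whole-number pair, with baseline from LLN to 75%, gives 100 uncovered pairs at LLN 50%, 127 at 53% and 140 at 55%. In each case the falls are 11 to 20 points and x runs from 40% to one point below LLN. These counts describe the shape of the table, not how often the event would occur.

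**Does the general table fill the gap?** Side by side for the same echo:

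| | Asymptomatic row, 11.3.4 | General table, Grade 2 | General table, Grade 3 |
|---|---|---|---|
| Interrupt | Required | To be considered | If clinically indicated |
| Repeat echo | Within 2 weeks | Not stated | Not stated |
| Condition for restart | Recovery within 4 weeks, plus approval | Grade 1 or baseline | Grade 1 or baseline |
| Restart dose | One level lower | Same | One level lower |

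The general table's Grade 4 row does require interruption, but Section 11.3.4 places Grade 4 at LVEF of 20% or lower, outside this band. Its rule to discontinue after a delay of 21 days or more takes effect only once treatment has been interrupted.

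**Timing.** Without the first row's instruction, the only fixed repeat is the routine echo: 3 cycles × 28 days = 84 days = 12 weeks. After an echo done exactly on schedule the next falls at 12 ± 2 = 10 to 14 weeks. If both echoes use their windows, the interval is 12 ± 4 = 8 to 16 weeks.

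**The case against.** The strongest reply is that no competent investigator would hold trametinib in an asymptomatic patient and continue it in one with the same echo plus pulmonary congestion, and that the protocol leaves ample room to act. Section 10.0 says that assessments should be more frequent when clinically indicated, and a below-normal LVEF with dyspnea is a clear indication, so 12 weeks is an unrealistic comparator. The opening of Section 11.0 ties dose changes to the nature, severity and attribution of the event and presents what follows as general guidance. Section 13.0 allows removal in the patient's best interest. The general table does make restart conditional on recovery. Which of its rows would apply depends on CTCAE grading criteria that the protocol does not reproduce, so how weak the fallback is cannot be settled exactly. The documents give no event frequency.

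Much of this stands. It limits the likely harm and means that the gap is a missing minimum rule, not an instruction to continue treatment. The routine interval is only what remains fixed by the calendar, not a forecast of care. But none of these provisions supplies the missing row. They leave to judgment, in the symptomatic patient, a hold that the protocol makes mandatory in the asymptomatic one. Neither plausible fallback row requires interruption, a repeat echo or approval to restart.

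**Conclusion.** The concern holds. Section 11.3.4 has no LVEF-specific instruction for a symptomatic fall of more than 10 and up to 20 points that ends below LLN and above 39%. That the gap exists follows from the table's own thresholds and holds for each LLN tried. Its width depends on the assumed LLN: at a baseline of 60% it is 40-49% for LLN of 50% or 55%; at 65% it is 45-49% or 45-54% respectively.

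The conclusion rests on reading the row labels as they stand. The practical effect is probably small: with a phase 2 maximum of 24 patients at a single institution, few are likely to fall in the band, though no frequency can be derived. The primary response analysis is not affected. The change should still be made, because it concerns a cardiac safety minimum and the present wording is least strict for the sicker patient.

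**What to change.** Amend the table so that the first row's actions are the minimum for any patient who meets its LVEF trigger, whatever their symptoms, unless the Grade 3/4 symptomatic row applies. Those actions are to interrupt trametinib, repeat the echocardiogram within 2 weeks, restart one level lower only on recovery and with approval, and otherwise discontinue. The sponsor may reasonably go further for symptomatic patients, for example by requiring a cardiology consultation at the outset; the first row requires one only after non-recovery.

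A clerical correction can go in at the same time. The word Symptomatic carries marker b, which leads to the re-escalation footnote. The definition of symptoms is footnote c, which has no marker in the table.

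The cost is a one-line amendment to one table and at most an occasional extra echocardiogram, which clinical practice may already call for. Sample size, endpoints and analysis do not change.

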11.3.5 QTc Prolongation

QTc prolongation has been observed in patients receiving trametinib. Therefore, 12 lead EKGs must be performed in regular intervals outlined in the Study Calendar.

Trametinib Withholding and Stopping Criteria for QTc Prolongation	
Prolongation*	Action and Dose Modification

 • QTcB ≥501 msec, or • Uncorrected QT >600 msec, or • QTcB >530 msec for subjects with bundle branch block 	
 • Interrupt study treatment until QTcB prolongation resolves to grade 1 or baseline. • Test electrolytes (K, Ca, Phos, Mg). If abnormal, replete to normal limits. • Review concomitant medication usage for a prolonged QTc • If the QTc prolongation resolves to grade 1 or baseline, trametinib may be resumed at current dose level • If the event does not resolve, permanently discontinue study treatment. • If the event recurs, permanently discontinue study treatment.

Trametinib Withholding and Stopping Criteria for QTc Prolongation	
Prolongation*	Action and Dose Modification
Abbreviations: msec = milliseconds; QTcB = QT interval on electrocardiogram corrected using the Bazett's formula	
* Based on average QTc value of triplicate ECGs. For example, if an ECG demonstrates a prolonged QT interval, obtain two or more ECGs over a brief period, and then use the averaged QTc values of the three ECGs to determine if study treatments should be interrupted or discontinued.	

11.3.6 Visual Changes

Episodes of visual changes have been observed in patients receiving trametinib. The causal relationship between a change in vision and the study treatment should be carefully explored and an ophthalmologist should be consulted. Patients are required to have a standard ophthalmic exam performed by an ophthalmologist at baseline and as clinically warranted. The exam will include indirect fundoscopic examination, visual acuity (corrected), visual field examination, tonometry, and direct funduscopy. Special attention should be given to retinal (e.g., CSR) or retinal vein abnormalities (e.g., RVO).

Guidelines regarding event management and dose reduction for visual changes considered to be related to study treatment are provided in the table below.

Management and Trametinib Dose Modification for Visual Changes		
Event CTCAE Grade	Management Guideline	Dose Modification
Any grade of CRS or RVO should be reported as SAE		
Grade 1 Asymptomatic or symptomatic but not limiting ADL; intervention not indicated.	
 • Consult ophthalmologist within 7 days of onset. • Exclude CSR or RVO. • Consult retinal specialist if available in case of CSR or RVO. • Continue follow up examination(s) (by retinal specialist if available) for CSR and RVO. 	
 • Continue trametinib at the same dose level until ophthalmologic examination can be conducted.* • If ophthalmologic examination cannot be performed within 7 days of onset, interrupt trametinib until CSR and RVO can be excluded and symptoms resolve. • If CSR and RVO excluded restart trametinib at same dose level. • If CSR: Interrupt trametinib until symptoms resolve and exam (by retinal specialist if available) shows resolution. May restart trametinib with one dose level reduction. • If RVO: Permanently discontinue trametinib.

Management and Trametinib Dose Modification for Visual Changes		
Event		
CTCAE Grade	Management Guideline	Dose Modification
Any grade of CRS or RVO should be reported as SAE		
Grade 2 and 3 Grade 2 defined as: Symptomatic with moderate decrease in visual acuity (20/40 or better; limiting instrumental ADL; local or non-invasive intervention indicated.) Grade 3 defined as: Symptomatic with marked decrease in visual acuity or marked visual field defect (worse than 20/40 but better than 20/200); severe pain or medically significant; operative intervention indicated.	
 • Consult ophthalmologist immediately. • Exclude CSR and RVO. • Consult retinal specialist in case of RVO or CSR for follow-up exam. • Continue follow up examination(s) (by retinal specialist if available) for CSR and RVO 	
 • Interrupt trametinib until signs and symptoms have resolved to baseline. • If CSR and RVO excluded and symptoms resolved to baseline, restart trametinib reduced by one dose level. • If CSR: Interrupt trametinib until symptoms resolve and exam (by retinal specialist if available) shows resolution. If CSR resolves restart trametinib reduced by one dose level. • If RVO: Permanently discontinue study treatment.
Grade 4 Sight-threatening consequences; urgent intervention indicated; blindness (20/200 or worse).	
 • Consult ophthalmologist immediately. • Exclude CSR and RVO. • Continue follow up examination(s) (by retinal specialist if available) for CSR and RVO. 	Permanently discontinue trametinib.
Abbreviations: CSR = central serous retinopathy; RVO = retinal vein occlusion; SAE = serious adverse event * If visual changes are clearly unrelated to study treatment (e.g., allergic conjunctivitis), monitor closely but ophthalmic examination is not required. * If ocular toxicities do not resolve within 21 days, permanently discontinue trametinib.		

11.3.7 Hypertension

Management and Dose Modification Guidelines for Hypertension

Hypertension	Action and Dose Modification
(Scenario A) 
 Asymptomatic and persistent^a SBP of ≥ 140 and < 160 mmHg, or DBP ≥ 90 and < 100 mmHg, or 
 Clinically significant increase in DBP of 20 mmHg (but DBP still < 100 mmHg). 	
 Continue trametinib at the current dose Adjust current or initiate new antihypertensive medication Titrate antihypertensive medication(s) during the next 2 weeks as indicated to achieve well-controlled^b BP If BP is not well controlled within 2 weeks, consider referral to a specialist and go to scenario (B).
(Scenario B) 
 Asymptomatic SBP ≥ 160 mmHg, or DBP ≥ 100 mmHg, or 
 Failure to achieve well-controlled BP within 2 weeks in Scenario A 	
 Interrupt trametinib if clinically indicated Adjust current or initiate new antihypertensive medication(s) Titrate antihypertensive medication(s) during the next 2 weeks to achieve well-controlled BP Once BP is well controlled^b, restart trametinib reduced by one dose level^c
(Scenario C) 
 Symptomatic^d hypertension or 
 Persistent SBP ≥ 160 mmHg, or DBP ≥ 100 mmHg, despite antihypertensive medication and dose reduction of trametinib 	
 Interrupt trametinib Adjust current or initiate new antihypertensive medication(s) Titrate antihypertensive medication during the next 2 weeks to achieve well-controlled BP Referral to a specialist for further evaluation and follow-up is recommended Once BP is well controlled, restart trametinib reduced by one dose level^c
(Scenario D) 
 Refractory hypertension unresponsive to above interventions, or having hypertensive crisis. 	
 Permanently discontinue trametinib Continue follow-up per protocol.

Abbreviations: BP = blood pressure; DBP = diastolic blood pressure; mmHg = millimetres mercury; SBP = systolic blood pressure;

- Hypertension detected in two separate readings during up to three consecutive visits
- Well-controlled blood pressure defined as SBP ≤ 140 mm Hg and DBP ≤ 90 mm Hg in two separate readings during up to three consecutive visits.
- Escalation of trametinib to previous dose level can be considered if BPs remain well-controlled for 4 weeks after restarting of trametinib. Approval from GSK Medical Monitor is required.
- Symptomatic hypertension defined as hypertension aggravated by symptoms (e.g., headache, light-headedness, vertigo, tinnitus, episodes of fainting) that resolve after the blood pressure is controlled within the normal range.

